# **10.1** Investigator Reporting Requirements

The investigator must immediately report (within 24 hours by telephone and followed by a written report sent by fax or e-mail) all serious adverse events to Renibus Therapeutics, Inc. regardless of whether the investigator believes that they are drug related, including those events

Protocol Number: REN-003 (Original)

Date: 25 March 2019

listed in the protocol as anticipated to occur in the study population independent of drug exposure (see Section 10.2).

These serious adverse events must be reported to:

[name], FASN, FNKF

**Medical Monitor** 

Renibus Therapeutics, Inc [name]

> [contact] [contact]

E-mail: [contact]

Because the investigator is knowledgeable about the human subject (e.g., medical history, concomitant medications), administers the investigational drug, monitors the subject's response to the drug, is aware of the subject's clinical state and thus may be sensitive to distinctions between events due to an underlying disease process versus events that may be drug-related, and may have observed the event, the investigator must include an assessment of causality (i.e., whether there is a reasonable possibility that the drug caused the event) in the report to Renibus Therapeutics, Inc Copies of each report to Renibus Therapeutics, Inc. will be kept in the investigator's study file.

The investigator is responsible for complying with their IRB's requirements for reporting serious adverse events. Any expedited safety report (i.e., serious unexpected suspected adverse reaction) received from Renibus Therapeutics, Inc. should be submitted to the IRB. Copies of each report and documentation of IRB notification will be kept in the investigator's study file.

The investigator must record non-serious adverse events in the eCRF and report them to Sponsor according to the timetable for reporting (e.g., end of study). The investigator's assessment of causality is not required for non-serious adverse events.

### 10.2 Definitions

Adverse Event: Adverse event means any untoward medical occurrence associated with the use of a drug in humans, whether or not considered drug related. An adverse event can be any unfavorable and unintended sign (e.g., an abnormal laboratory finding), symptom, or disease temporally associated with the use of a drug, without any judgment about causality.

Adverse Reaction: Adverse reaction means any adverse event definitely caused by the drug.

Suspected Adverse Reaction: Suspected adverse reaction means any adverse event for which there is a "reasonable possibility" (i.e., evidence indefinite but suggests a causal relationship between the drug and the adverse event) that the drug caused the adverse event. By definition, a suspected adverse reaction is identical to the definition of adverse drug reaction per ICH E2A.

Protocol Number: REN-003 (Original)

Date: 25 March 2019

Examples that would suggest a causal relationship:

- A single occurrence of an event that is uncommon and known to be strongly associated with drug exposure (e.g., angioedema, hepatic injury, Stevens-Johnson Syndrome)
- One or more occurrences of an event that is not commonly associated with drug exposure, but is otherwise uncommon in the population exposed to the drug (e.g., tendon rupture)
- An aggregate analysis of specific events observed in a clinical trial (e.g., known consequences of the underlying disease or condition under investigation or other events that commonly occur in the study population independent of drug therapy) that indicates those events occur more frequently in the drug treatment group than in a concurrent or historical control group.

Unexpected Adverse Event or Unexpected Adverse Reaction: An adverse event or adverse reaction is considered "unexpected" if it is not listed in the investigator brochure or is not listed at the specificity or severity that has been observed.

Adverse events or adverse reactions that are mentioned as occurring with a class of drugs or as anticipated from the pharmacological properties of the drug will be considered "unexpected" if they are not specifically mentioned as occurring with the particular drug under investigation.

Until the investigator brochure is updated to include a new serious suspected adverse reaction, subsequent occurrences of similar serious suspected adverse reactions must be submitted expeditiously to FDA in IND Safety Reports and to other appropriate regulatory authorities in countries other than the US in an Individual Case Safety Report (ICSR) or using a Council for International Organizations of Medical Sciences (CIOMS) I form, as appropriate.

Serious Adverse Event or Serious Adverse Reaction: An adverse event or adverse reaction is considered "serious" if, in the view of either the investigator or Sponsor, it results in any of the following outcomes:

- Death
- A life-threatening adverse event
- In subject hospitalization or prolongation of existing hospitalization
- A persistent or significant incapacity or substantial disruption of the ability to conduct normal life functions
- A congenital anomaly/birth defect.

Important medical events that may not result in death, be life-threatening, or require hospitalization may be considered serious when, based upon appropriate medical judgment, they may jeopardize the subject and may require medical or surgical intervention to prevent one of the outcomes listed in this definition.

If either the investigator or Sponsor believes that the event is serious, it must be evaluated by the Sponsor for expedited reporting to regulatory authorities.

Life-Threatening Adverse Event or Life-Threatening Adverse Reaction: An adverse event or suspected adverse reaction is considered "life-threatening" if, in the view of either the investigator or Renibus, its occurrence places the subject at immediate risk of death.

Protocol Number: REN-003 (Original)

Date: 25 March 2019

Serious Unexpected Suspected Adverse Reaction: An adverse event for which there is a reasonable possibility that the drug caused the adverse event, and it is not listed in the investigator brochure or is not listed at the specificity or severity that has been observed, and it results in any of the serious outcomes listed above. This criterion is consistent with the concepts of FDA 21 Code of Federal Regulation (CFR) 312 and the ICH E2A Guideline for expedited safety reports.

The Sponsor must notify the appropriate regulatory authority(ies) and all participating investigators in an expedited safety report (e.g., IND Safety Report or ICRS) of potentially serious risks from clinical trials or any other source (i.e., a serious unexpected suspected adverse reaction), as soon as possible, but no later than 15 calendar days after Renibus Therapeutics, Inc. receives the safety information and determines that the information qualifies for reporting.

During the course of drug development, the Sponsor may become aware of new safety information from a variety of sources and will decide if an individual case of a serious and unexpected adverse event meets the criteria for reporting to regulatory authorities.

If the adverse event does not meet all criteria (i.e., reasonable possibility of causality, serious and unexpected), it should not be submitted as an expedited safety report.

Any unexpected fatal or life-threatening suspected adverse reaction must be reported to regulatory authorities no later than 7 calendar days after Renibus Therapeutics, Inc. receives the safety information.

# 10.3 Breaking the Blind

Not applicable as this is an open label study.

# 11 STATISTICAL CONSIDERATIONS

This section outlines the nature and rationale for the statistical methods to be used for the analysis of the data from the study. A separate Statistical Analysis Plan (SAP) will describe data handling and statistical techniques in full detail.

### 11.1 Study Populations

All subjects who receive study medication will be included in the safety and PD analyses. All subjects who receive study medication and provided sufficient and valid serum SnPP concentration data to allow the determination of PK parameters will be considered as potential PK evaluable subjects. No imputation will be used for missing data.

# 11.2 Demographic and Baseline Characteristics

Demographic and baseline variables that will be summarized by dose group include:

- Demographics
- Medical history
- Complete PE
- Efficacy and Safety variables including vital signs and laboratory tests, including chemistry, hematology, and urinalysis obtained at Screening.

Protocol Number: REN-003 (Original)

Date: 25 March 2019

# 11.3 Analysis of Efficacy Endpoints

Descriptive statistics will be used to summarize Response biomarker results at baseline, each visit, and the change from baseline for each visit.

Percent change from baseline will be analyzed using the mixed model for repeated measures (MMRM). In this analysis, percent change from baseline at each post treatment time point will be the response variable; treatment, visit, and treatment-by-visit interaction as fixed factors, patient as repeated measure unit over visits, and baseline as covariate. The between-group comparison will be performed using the simple contrast at 2, 4, 8, 12, 18, 24, 48, 72, 96 and 168 hours post-dosing.

In addition to the percent changes from baseline, absolute change from baseline will also be analyzed using MMRM. Moreover, a responder analysis will also be considered. The responder definition and its appropriate analysis methodology will be detailed in the statistical analysis plan (SAP) for the study. Exploratory analysis using Cochran-Mantel-Haenszel test stratified by baseline or primary diagnosis will be carried out.

# 11.4 Analysis of Pharmacodynamic/Safety Endpoints

The evaluation of safety will include adverse events, clinical laboratory parameters, vital signs, physical examinations, and ECGs.

The principle of treatment emergence will be employed for the analysis of adverse event data. A Treatment emergent adverse event (TEAE) is defined to be any event that occurs during the observation period of the study and was not present at baseline, or exacerbation of a condition present at baseline.

TEAEs will be classified by the Medical Dictionary for Regulatory Activities (MedDRA). The type, incidence, timing (onset, duration), relationship, and severity of adverse events will be reported for treatment-emergent and serious adverse events. Reasons for withdrawal due to adverse events will also be reported.

Descriptive statistics, including mean, mean change from baseline, standard deviation, minimum, maximum, and median, will be presented for laboratory parameters, vital signs, and ECG parameters. The numbers and percentages of subjects with treatment-emergent laboratory, vital sign, and ECG values that meet Sponsor-defined potentially clinically significant criteria will be summarized. Categorical (low, normal, and high relative to the normal range) shifts from baseline will be summarized with the number and percentage of subjects for laboratory parameters.

All safety data will be displayed in listings.

# 11.5 Analysis of Pharmacokinetic (PK) Data

Pharmacokinetic (PK) parameters will be calculated for each subject and summarized by treatment group. PK profiles in which the pre-dose concentration is > 5% of the corresponding  $C_{max}$  (and therefore greater than the lower limit of quantification [LLOQ]) will be excluded from all descriptive statistics and statistical analyses.

For the PK analysis performed, actual blood sampling times will be used in all PK analyses. Protocol-specified times will be used to calculate mean plasma or serum concentrations for

Protocol Number: REN-003 (Original)

Date: 25 March 2019

tabular and graphical displays. All PK calculations and generation of individual subject plasma or serum concentration versus time graphs will be performed using SAS®.

PK parameters will be calculated using non-compartmental analysis. The maximum serum concentration ( $C_{max}$ ) and time to maximum serum concentration ( $T_{max}$ ) will be obtained directly from the data. The elimination rate constant ( $\lambda z$ ), elimination half-life ( $T_{1/2}$ ), area under the concentration-time curve from time 0 to time t ( $AUC_{[0-inf]}$ ) and area under the concentration-time curve from time 0 to infinity ( $AUC_{[0-inf]}$ ), clearance (CL), and volume of distribution (Vz) will be calculated for each subject and summarized by treatment group. Only plasma samples with concentrations  $\geq LLOQ$  will be used in the PK analysis. Plasma concentrations  $\leq LLOQ$  will be taken as 0 for the calculation of the descriptive statistics at each sampling time. For the PK analysis, plasma concentrations  $\leq LLOQ$  that occur from pre-dose to the first concentration  $\geq LLOQ$  will be taken as 0 and those that occur thereafter will be taken as missing.

The first dose escalation, from 9 mg to 27 mg, will be based on assuming a dose-proportional increase in Cmax and AUC and will use the maximum values across the first cohort. The subsequent decisions to escalate to the next dose level will be based on the available pharmacokinetic exposure data from the previous dose cohort(s) and compared with the exposure levels at the NOAEL established in the acute dose toxicity study in male and female Sprague Dawley rats. The dose escalation decision will utilize best available modelling practices, i.e. fitting the power model to the individual subject Cmax and AUC vs. dose. A dose will not be administered that would result in an upper 95th percentile for the model-predicted Cmax and AUC values exceeding 39,250 ng/mL and 209,500 hr.ng/mL (mean of males and females), respectively. These values were the observed values at the NOAEL of 10 mg/kg/day in the GLP toxicology study performed in Sprague Dawley rats.

### 11.6 Sample Size Calculations

No formal sample size calculation has been performed for the study. However, it is believed that 4 subjects per dose group will be adequate to establish POC based on biomarker response and identify an optimal dose for further testing, recognizing that a battery of different surrogate biomarkers will be evaluated.

# 11.7 Interim Analysis

No interim analysis is planned.

# 12 WITHDRAWAL FROM STUDY

Every reasonable effort should be made to maintain protocol compliance and participation in the study. Should a subject withdraw or be prematurely terminated from the study for any reason, the reason for early study withdrawal will be recorded. If withdrawal is the result of a serious

Protocol Number: REN-003 (Original)

Date: 25 March 2019

adverse reaction, the subject will be followed until the condition has resolved, as determined by the investigator.

The investigator or Sponsor may withdraw any subject at any time for medical reasons or for administrative reasons (i.e., subjects unable or unwilling to comply with the protocol). If so, the subject will be censored at time of withdrawal and, if possible, a final evaluation (End of Study procedures) will be made. All treated subjects (those who have received at least 1 dose of investigational product) will be included in the ITT and safety analyses.

In the unlikely event the Sponsor or FDA should determine it is appropriate to terminate the study early, every effort will be made for transitioning subjects with minimal disruption to the subject and investigator. The IRB will be notified of termination, and reason(s) and procedures for follow-up of research subjects will be developed by the study physician in consultation with the Sponsor and IRB.

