- Haptoglobin, Ferritin, Bilirubin, Hemopexin, IL-10, P21 and HO-1.
-  Cystatin-C, IL-6, SnPP, total porphyrin, Tin, Troponin I, albuminuria, Kidney Injury Molecule-1 (KIM-1), Neutrophil Gelatinase-Associated Lipocalin (NGAL), N acetyl-beta-D-glucosaminidase (NAG), (in addition to BUN/Cr which are part of the Serum Chemistry panel)
- Three measurements will be taken for the urinary safety biomarkers (albuminuria, Kidney Injury Molecule-1 (KIM-1), Neutrophil Gelatinase-Associated Lipocalin (NGAL), and N acetyl-beta-D-glucosaminidase (NAG)), eGFR, and response biomarkers prior to dosing.
- \*\* Day 14 safety evaluation will be conducted at the request of the DSMB after each cohort safety review

Protocol Number: REN-003 (Original)

Date: 25 March 2019

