- After a careful review of the safety, tolerability and PK data from all dose groups from the stage 3 CKD cohorts, the Data and Safety Monitoring Board (DSMB) will determine whether to proceed to the stage 4 CKD cohorts. If the determination by the DSMB allows to proceed to the stage 4 CKD cohorts, subjects with stage 4 CKD will be in 2 groups of 6 each, for a total of 12 subjects, evaluating escalating single dose of SnPP starting with a dose of 27 mg SnPP followed by 90 mg SnPP. Dose-escalation from one dose level to the next will only be allowed after a careful review of the safety, tolerability and PK data from the prior dose group as determined by the Data and Safety Monitoring Board (DSMB).
- The infusions will be given over a 120-minute period using a syringe pump.
- Subjects will be followed for 28 days after the dose of SnPP. Response and Safety biomarkers will be assessed at baseline and (2, 4, 8, 12, 18, response biomarkers only) 24, 48, 72, 96 and 168 hours after study drug administration. Safety will be assessed for up to 28 days after study drug administration. Urine samples will be collected and centrifuged and analyzed for subject responsiveness to SnPP therapy.
- Blood samples for pharmacokinetic analysis will be collected at baseline and 1, 2, 3, 4, 6, 8, 12, 18 and 24 h post start of infusion.
- Urinary excretion of SnPP will be assessed in a 24-hour urine sample by measuring tin in urine
- Total study duration will be up to 29 days per subject.

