# 9.6.7 Study Day 29/End of Study Visit ( $28 \pm 1$ days following the SnPP dose)

- 1. Subjects will arrive at the clinic at 8:00am ( $\pm$  60 minutes).
- 2. Blood samples for standard assessment of clinical chemistry, hematology, and safety biomarkers will be collected (Appendix 1).
- 3. Urine samples for standard assessment of urinalysis parameters and safety biomarkers will be collected (Appendix 1).
- 4. A full physical examination including weight and vital signs will be performed (Sections 9.8.3 and 9.8.4).
- 5. The clinic staff will solicit any adverse events and note any changes in concomitant medications since the last visit
- 6. A urine pregnancy test will be performed if the subject is a woman of childbearing potential.

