# 10 ADVERSE EVENT REPORTING

All adverse events will be recorded on the designated study eCRF for each subject beginning with the first administration of investigational product and ending with the date of the end of study treatment follow-up. Any unresolved adverse events will be followed by the investigator until event resolution, the subject is lost to follow-up, the adverse event is otherwise explained or not considered clinically significant by the investigator.

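### Protocol section 12 can end new adverse-event collection and the remaining safety tests before Day 29 for a dosed subject whom the investigator or sponsor withdraws

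*Protocol*

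**What the plan says.** Protocol section 12 lets the investigator or sponsor withdraw any subject at any time, for medical or administrative reasons. It continues: "If so, the subject will be censored at time of withdrawal and, if possible, a final evaluation (End of Study procedures) will be made". The same section opens with a general aim, "Every reasonable effort should be made to maintain protocol compliance and participation in the study", and keeps dosed subjects in the analysis: "All treated subjects (those who have received at least 1 dose of investigational product) will be included in the ITT and safety analyses". If a serious adverse reaction caused the withdrawal, the subject is followed until that condition resolves.

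Other sections that bear on the point:

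- Protocol 9.3 sets the follow-up: "Subjects will be followed for 28 days after the dose of SnPP".
- Protocol 5.1 and 9.6 fix post-dose visits on Days 2, 3, 4, 5, 8 and 29. Day 14 is conditional: "Day 14 safety evaluation will be conducted at the request of the DSMB after each cohort safety review".
- Protocol 9.6.7 says of the End of Study visit: "The clinic staff will solicit any adverse events and note any changes in concomitant medications since the last visit".
- Protocol 10 records adverse events from first administration to the end of follow-up, and adds: "Any unresolved adverse events will be followed by the investigator until event resolution". It allows exceptions, such as loss to follow-up.
- Protocol 10.1 requires the investigator to report "all serious adverse events to Renibus Therapeutics, Inc. regardless of whether the investigator believes that they are drug related".
- SAP 5 defines a treatment-emergent event by onset at or after the start of infusion, with no cut-off at withdrawal. SAP 6 puts every dosed subject in the safety population. SAP 7.1 bases percentages on the number of subjects in the population.

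**The concern.** Safety and tolerability is the first primary objective (Protocol 7.1), and the DSMB reviews safety in each dose group of 6 before escalation. Drug exposure has already happened by the time a dosed subject is withdrawn, so the safety question for that subject stays open to Day 29. The censoring sentence treats withdrawal as an end point and makes the substitute evaluation optional.

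The stake is a mismatch in the adverse-event tables. A withdrawn subject who is no longer asked about events stays in the denominator and cannot add to the numerator. Laboratory summaries report n, so missing values show there, but the data are still lost. Withdrawal for medical reasons may be related to safety, so the loss need not be random. The one risk that Protocol 6.4 describes, photosensitivity on exposure to sunlight or UV-A after dosing, can appear after discharge on Day 2. After Day 8, Day 29 is the only safety visit fixed for everyone.

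**Working it through.** The plan states no withdrawal or late-event rate, so there is no figure to reproduce. The check has two parts.

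**1. Does any rule require new-event collection after such a withdrawal?**

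| Provision | What it covers | What it leaves open |
|---|---|---|
| Protocol 9.3, 28-day follow-up | Subjects in the study | Whether it survives the censoring clause |
| Protocol 9.8, monitoring throughout the study | Subjects in the study | The same |
| Protocol 10, recording window | To the end of follow-up | Withdrawal may itself be that end |
| Protocol 10, unresolved events | Events already open | New events |
| Protocol 10.1 | Serious events known to the investigator | No duty to ask; non-serious events |
| Protocol 12, serious adverse reaction | The condition behind the withdrawal | Other withdrawals; new events |
| Protocol 12, final evaluation | One full set of tests, events since the last visit | Only if possible; no time stated |
| SAP 5, treatment-emergent definition | Counts any recorded event | Collects nothing |

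No row requires new events to be sought, or the remaining safety tests to be done, up to Day 29 after this kind of withdrawal.

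**2. Scale, for illustration only.**

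Inputs: follow-up to Day 29, 28 days after the dose; six fixed post-dose visits (Days 2, 3, 4, 5, 8, 29). Withdrawal is taken to follow any visit due that day.

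Days unobserved if contact ends at withdrawal = 29 − withdrawal day; share = that number / 28.

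| Withdrawal day | Days unobserved if contact ends | Share | Fixed visits lost if contact ends | Fixed visits lost if the final evaluation is made at Day 29 |
|---|---|---|---|---|
| 2 | 27 | 96% | 5 of 6 | 4 of 6 |
| 5 | 24 | 86% | 2 of 6 | 1 of 6 |
| 8 | 21 | 75% | 1 of 6 | 0 of 6 |
| 15 | 14 | 50% | 1 of 6 | 0 of 6 |

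A final evaluation made at withdrawal keeps one set of tests but looks back, so it recovers none of the unobserved days. Made at Day 29, it asks about the whole gap and recovers most of what would be lost.

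Effect on incidence: let p be the later-event risk, equal for all, with 1 of n subjects unobserved. Expected recorded incidence = (n − 1)p / n = p(1 − 1/n), a relative understatement of 1/n.

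- Healthy-volunteer dose group, n = 6: 1/6 = 17%
- CKD dose group over both stages, n = 6 + 6 = 12: 1/12 = 8%
- 27 mg or 90 mg over all populations, n = 6 + 12 = 18: 1/18 = 6%

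At an assumed p of 10% and n = 6, recorded incidence would be 10% × 5/6 = 8.3%, a shortfall of 1.7 percentage points.

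Chance of seeing at least one late event = 1 − (1 − p)^n:

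- p = 10%: 46.9% with 6 observed, 41.0% with 5
- p = 20%: 73.8% with 6 observed, 67.2% with 5

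One-sided 95% upper bound after zero events = 1 − 0.05^(1/n): 39.3% with 6, 45.1% with 5.

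**The case against.** The strongest reply is that censoring is an analysis term. The protocol does not define it, and the sentence does not say that visits or adverse-event recording stop. The SAP supersedes the protocol's statistical methods and sets no withdrawal cut-off. A reader might therefore infer too much: that sites are told to drop withdrawn subjects, or that later events would be discarded. The documents support neither. A later event that is recorded would be counted. What stands is narrower. The trial has no time-to-event endpoint, so the word has no evident analytic role here, and even on the analysis reading nothing requires collection to continue.

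A reader might also take the day-loss figures as the expected loss. They are not. Section 12 gives no time for the final evaluation, and the End of Study visit is defined elsewhere as 28 ± 1 days after the dose. If it is made then, most of the gap closes.

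Third, few subjects are exposed. Those withdrawn for non-compliance may not attend under any wording, and many medical withdrawals would leave an open event that is followed anyway. The remainder is mainly a cooperative subject with a new, non-serious event or a missed later test. An early exit would also be visible, because SAP 7.2 tabulates discontinuations with reasons and individual data are listed. All of this stands. It limits the size of the problem but does not supply the missing instruction.

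**Conclusion.** The point holds as a gap in data collection. For a dosed subject withdrawn by the investigator or sponsor, section 12 as written can end the search for new adverse events and the remaining safety tests before Day 29, while the subject stays in the denominator. It is probably small, and it is zero if no dosed subject is withdrawn. The 1/n figures assume one affected subject, no contact after withdrawal and equal risk; the documents give none of these. It would go too far to conclude that the safety results or the DSMB's escalation decisions are unreliable, because without a withdrawal rate nothing in the documents shows a material effect. This is a cheap improvement in support of the first primary objective.

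**What to change.** In Protocol section 12, replace the censoring sentence with:

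> Withdrawal by the investigator or sponsor after any SnPP does not end safety follow-up: AE collection and the remaining scheduled safety visits continue to Day 29 unless the subject withdraws consent, cannot be reached, or the investigator judges a procedure medically inappropriate; in that case End of Study procedures are done at withdrawal if possible.

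Two SAP edits go with it:

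- **Sections 5 and 7.2:** count such subjects as discontinued and not as Completers. Otherwise a withdrawn subject seen at Day 29 would meet the Completer definition and also be tabulated as discontinued.
- **Section 7.1.1.2:** impute unknown adverse-event stop dates from the date of last safety contact. The present rule uses the discontinuation date when the year is unknown and the discontinuation month when the month is unknown. Either can fall before the onset of an event that starts after withdrawal.

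The cost is one protocol sentence and two small SAP edits. No visit or test is added, because all are already scheduled for every subject. Some withdrawn subjects would be asked to attend those visits, and those withdrawn for non-compliance may not come, so part of the gap would remain.
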